### 3. Sample Size and Statistical Analysis

#### 3.1. Sample size

With a sample size of n=338 (169 women per group) we will be able to detect a difference between two independent proportions of LGA of 13.7% vs 25.8% (according to the results of a previous study) with a power of 80% and a two-sided type 1 error of  $\alpha=0.05$  (calculated for Pearson's chi-square test). Considering a drop-out rate of 10% a total sample size of n=372 (186 women per group) is necessary for this study. This is in line with the sample size suggested by Kestilä et al.. A blinded sample size review (the proportion of LGA cases in the sample is reviewed) and adaptation is planned after 50% of the patients have been investigated. The sample-size calculation was performed by using the software G\*Power (V3.1.9.2).

#### 3.2. Analysis plan

Analyses should be conducted on the intention-to-treat principle. Categorical variables will be summarized by counts and proportions; continuous variables data will be summarized by means and standard deviations (SD) or by median and interquartile range in the case of strong deviations from the normal distribution. Pearson's chi-square test will be used to compare differences in the primary outcome (difference in proportion of LGA newborns) and for binary secondary outcomes (such as caesarean section rate, shoulder dystocia and neonatal hypoglycaemia). Bernard's test will be used as an alternative if an expected frequency in contingency tables is equal or less than 5 and the Cochran-Mantel-Haenszel method will be used as sensitivity analysis to adjust for possible center specific effects. Continuous secondary outcome parameters (such as mean glucose, duration and amount of hyperglycaemia, glycaemic variability and other CGM measures, postpartum OGTT data, HbA1c, glycosylated fibronectin, hsCRP, proBNP, Troponin T, or anthropometric data of the newborn) will be compared by student's t-test. Rank based inference (such as the Brunner-Munzel test) will be used as an alternative in case of skewed distributed parameters. The association between HbA1c, CGM measures and delivery and risk of LGA offspring will be assessed by binary logistic regression. There are many possible objectives for which analysis could be performed in this study (e.g. functional principal components analysis for CGM data). Hence, the present analysis plan represents only a selection of methods, which will be used for analysing the main objectives. Risk and time preferences will be analysed by non-parametric and parametric methods. In particular, we plan to fit the choice data to a CRRA (constant relative risk aversion) utility function. Associations between risk and time preferences and behaviour (dietary patterns and physical activity) will be investigated. For the health economic evaluation, incremental cost-effectiveness and cost-utility ratios (ICER/IUCR: additional cost per additional LGA

newborn avoided or per quality-adjusted life year gained) will be calculated. 95% confidence intervals will be analysed using bootstrap procedures. To consider uncertainty, univariate and probabilistic sensitivity analyses will be performed and cost-acceptability curves will be created. A two-sided p-value  $\leq 0.05$  is considered statistically significant. All analyses will be performed by using the statistic software R and contributing packages. No further adjustment for multiplicity is planned for this study.

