### *2.4. Randomisation*

Participants will be randomized to either treatment (rt-CGM augmented glucose monitoring) or control group (routine care SMBG) in a 1:1 ratio. The minimisation method with a 0.85 assignment probability will be used to minimize the imbalance between the groups according to week of gestation at study entry i.e. at V1 (three strata: 24+0 to 25+6, 26+0 to 27+6, 28+0 to 29+6, 30+0 to 31+6), previous pregnancy with GDM (two strata: yes or no) and preconceptional overweight/obesity status with three strata: i. normal weight (i.e. BMI below  $25.0 \text{ kg/m}^2$ ); ii. overweight ( $\text{BMI } 25.0 - 29.9 \text{ kg/m}^2$ ); iii. obesity ( $\text{BMI equal or above } 30.0 \text{ kg/m}^2$ ). Randomisation will be performed at the second study visit (V2) by using the "MUW Randomizer" software.

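### The primary LGA test leaves out the three minimisation factors; if they predict LGA it is slightly conservative and gives up a little power that adjustment would recover without extra patients

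*Combined protocol and SAP*

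**What the plan says.** Section 2.4 (Randomisation) uses minimisation with assignment probability 0.85, which "will be used to minimize the imbalance between the groups according to week of gestation at study entry", previous GDM (yes or no) and preconceptional BMI class (three levels). The week factor is described as "three strata: 24+0 to 25+6, 26+0 to 27+6, 28+0 to 29+6, 30+0 to 31+6", which is four bands.

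Section 3.1 (Sample size) powers the trial for a "difference between two independent proportions of LGA of 13.7% vs 25.8" per cent "with a power of 80% and a two-sided type 1 error of" 0.05, for Pearson's chi-square test with 169 women per group.

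Section 3.2 (Analysis plan) says that Pearson's "chi-square test will be used to compare differences in the primary outcome", the LGA proportion. Two other analyses come near the point, and neither uses the minimisation factors to compare treatments:

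- The "Cochran-Mantel-Haenszel method will be used as sensitivity analysis to adjust for possible center specific effects". Centre is not one of the minimisation factors.
- "The association between HbA1c, CGM measures and delivery and risk of LGA offspring will be assessed by binary logistic regression". As written, this is not a treatment comparison.

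**The concern.** Minimisation forces the two arms to be alike on the three factors. If those factors predict LGA, the difference in LGA proportions varies less from trial to trial than it would under simple randomisation. An unadjusted chi-square takes no account of this. Its standard error still contains the between-stratum variation that the design has removed, so the test rejects less often than 5% under the null and loses some power under the alternative.

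At stake is efficiency, not validity. The error is on the conservative side, and if the factors do not predict LGA there is nothing to recover. The point still deserves attention because the trial is planned at almost exactly 80% power, on LGA rates taken from a study that section 1.1 describes as non-randomised and observational. Section 3.2 also calls itself only a selection of methods. An adjusted analysis is therefore neither specified nor excluded, and covariates chosen after unblinding would be open to doubt.

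**Working it through.** **1. The plan's own figure.** Inputs from section 3.1: rates 0.258 and 0.137, n = 169 per group, two-sided α = 0.05.

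- Difference D = 0.121; mean rate (0.258 + 0.137)/2 = 0.1975.
- Pooled SE: s_p = √(2 × 0.1975 × 0.8025/169) = 0.04331.
- Unpooled SE: s_u = √((0.258 × 0.742 + 0.137 × 0.863)/169) = 0.04281.
- Power = Φ((0.121 − 1.96 × 0.04331)/0.04281) = Φ(0.844) = 80.06%.

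The 169 per group reproduces.

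**2. Closed form, without odds ratios.** Suppose the factors explain a share R² of LGA variance and are perfectly balanced. The true SD of the difference is multiplied by k = √(1 − R²); the chi-square SE is not.

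- Chi-square type I error = 2(1 − Φ(1.96/k)).
- Chi-square power = Φ((D − 1.96 s_p)/(k s_u)).
- Adjusted power = Φ((D − 1.96 k s_p)/(k s_u)).

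At R² = 5%, k = 0.9747. Type I error is 2(1 − Φ(2.011)) = 4.4%. Power is Φ(0.866) = 80.7% unadjusted and Φ(0.917) = 82.1% adjusted.

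| R² | Chi-square type I error | Gain in power from adjusting (points) |
|---|---|---|
| 0% | 5.0% | 0 |
| 3% | 4.7% | 0.8 |
| 5% | 4.4% | 1.4 |
| 10% | 3.9% | 2.7 |

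**3. Simulation of the actual allocation.** From the documents: 338 women, Pocock-Simon minimisation at 0.85 on the three factors, 25.8% vs 13.7% (null: 19.75% in both arms). Assumed, because the documents do not give them: four equally frequent week bands, previous GDM 20%, BMI classes 40/30/30%, and the odds ratios shown. There were 40,000 trials per cell; Monte Carlo SE is about 0.11 points for type I error and 0.20 for power. The adjusted test is the Wald test of treatment in a three-factor logistic model.

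| Prognostic strength (OR overweight/obese; previous GDM) | Type I error: chi-square | Type I error: adjusted | Power: chi-square | Power: adjusted |
|---|---|---|---|---|
| None | 5.04% | 5.04% | 80.66% | 80.64% |
| Weak (1.2/1.5; 1.3) | 4.93% | 5.05% | 80.73% | 80.99% |
| Moderate (1.5/2.2; 2.0) | 4.79% | 5.20% | 80.83% | 81.67% |
| Strong (2/4; 2.5) | 4.20% | 5.08% | 81.65% | 83.64% |

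The table names odds ratios for two of the three factors. A separate simulation with gestational week given no effect (6,000 trials per cell) agrees within Monte Carlo error. For none/weak/moderate/strong, chi-square type I error was 5.0/5.3/4.5/4.2%, and power was 79.5/80.9/81.1/81.1% unadjusted against 79.6/81.0/81.9/83.3% adjusted.

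**4. In women.** Power is 80.06% at 169 per group and 83.71% at 186, so one more woman per group is worth about (83.71 − 80.06)/17 = 0.215 points. The moderate gain is 0.84/0.215 ≈ 4 women per group; the strong gain is 1.99/0.215 ≈ 9.

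**5. Stronger effects, with week prognostic.** A further simulation (6,000 to 8,000 trials per cell) used odds ratios 1.6/2.7 for BMI, 2.0 for previous GDM and up to 1.35 for week, giving R² of about 0.05. Chi-square type I error was 4.6% and power 81.3% vs 82.4% adjusted. With larger effects, R² of about 0.11 gave 4.1% and 81.2% vs 84.1%. Doubling the log odds ratios (obesity about 2.7² ≈ 7, previous GDM 2.0² = 4; R² about 0.17) gave 3.7% and 82.5% vs 86.6%.

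**6. Can the model be fitted, and does it keep the estimand?** Expected events are 338 × 0.1975 ≈ 67, for 1 + 3 + 1 + 2 = 7 coefficients besides the intercept, which is workable. At R² of about 0.05 the standardised risk difference averaged −0.121, the same as the raw difference in proportions. With an influence-function variance, its test ran at 5.07 to 5.21% with an n/(n − p) correction and at 5.35 to 5.54% without.

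**The case against.** The strongest reply is that nothing in the plan is wrong. The chi-square is a legitimate test, matches the sample-size calculation and addresses the stated difference in proportions. The gain starts at zero and rests wholly on assumed prognostic strengths. Uncertainty in the borrowed LGA rates probably matters more, and section 3.1 already plans a blinded sample size review. An adjusted sensitivity analysis beside the Cochran-Mantel-Haenszel one might be a proportionate request.

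Much of this stands, and it is why the point is an improvement to consider rather than an error to correct. It does not remove the case for changing the primary test: no scenario showed a loss beyond simulation error, and an adjusted sensitivity analysis would not recover power for the primary conclusion.

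Three narrower objections also have substance. First, adjustment is not free of drafting: the uncorrected robust variance ran slightly above 5%, so the variance method must be fixed in advance. Second, the logistic model tests a conditional odds ratio while a marginal risk difference is reported, so the plan must say which inference is primary; the two tests disagreed in only about 0.1% of simulated trials. Third, the four week bands are contiguous with explicit limits, so the stated count of three may be a simple miscount. It is a wording matter to settle and adds no weight to the efficiency argument.

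**Conclusion.** The point holds as a modest loss of efficiency. No planned treatment comparison uses the factors by which the trial allocates. The chi-square remains valid and the stated 80% power is met. Under the assumed weak-to-strong scenarios, its type I error is about 4.9% to 4.2% and it gives up about 0.3 to 2.0 points of power; with no prognostic value it gives up nothing. Only very strong effects (R² of about 0.17) bring the loss to about 4 points.

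Confidence is medium. The mechanism and direction are certain, but the size depends on factor frequencies and prognostic strengths that the documents do not give.

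**What to change.** - Pre-specify the primary analysis as a logistic regression of LGA on treatment and the three minimisation factors, with the test of the treatment term as the primary test.
- Report the standardised risk difference and risk ratio with 95% confidence intervals, so that the effect measure stays a difference in proportions. Name the variance method; an influence-function variance with an n/(n − p) correction performed well here.
- Keep the chi-square as supportive, say what is done if the model does not converge, and leave centre in the planned Cochran-Mantel-Haenszel sensitivity analysis.
- Before that, reconcile the stated number of week strata in section 2.4 with the four bands listed, and state how the factor is coded in the model.
- Use the same model for binary secondary outcomes with enough events, and keep the planned tests for sparse ones.

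The cost is analysis-plan wording and a few lines of R. The covariates are already collected for the randomiser, and no patients or visits are added. The change should be made before unblinding.

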**Outcomes:** Differences in the proportion of LGA newborns (birth weight >90. pct) in women with GDM using rt-CGM as compared to women with GDM using SMBG will be assessed as the primary outcome. Differences in neonatal hypoglycemia, rate of caesarean section, shoulder dystocia and neonatal anthropometry will be assessed as secondary outcomes. Further secondary outcomes are: differences in neonatal hyperinsulinemia, CGM measures such as mean interstitial glucose, glucose variability, time in range as well as time spent in hyper- and hypoglycemia (day- and night-time), duration and frequency of postprandial hyperglycaemic excursions, start and amount of glucose lowering therapy, HbA1c, change in bodyweight during pregnancy and after delivery, glucose disposal at postpartum (markers of insulin sensitivity, insulin secretion and  $\beta$ -cell function assessed by a postpartum OGTT), as well as health-related quality of life, and patients' risk- and time preferences and its association with adherence to dietary and exercise recommendations.

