## *2.2. Study visits pregnancy*

A broad risk evaluation will be performed in participating females at the initial contact (V1) including: evaluation of maternal age, parity, history of GDM in previous pregnancies, detailed family history, ethnicity, preconceptional diseases, obstetric history. Height (stadiometer measured to the nearest centimeter) and actual weight (calibrated scales, no clothes) will be additionally assessed. Moreover, an evaluation of preconceptional weight (self-reported) and BMI as well as measurement of blood pressure will be performed. All patients receive medical nutrition therapy (isocaloric diet containing 40-50% carbohydrates, 20% proteins and 30-35% fat, divided into three meals and three snacks) and lifestyle advice for 30 minutes following international recommendations and are advised on capillary blood glucose measurement (fasting as well as 1h after starting each meal) at the initial visit (V1). Randomisation will be done after a run-in period of 6 to 8 days (V2). The run-in period is omitted for patients who had a diagnosis of GDM before 24+0 according to the local guidelines and already received medical nutrition therapy, lifestyle intervention and advices on capillary blood glucose measurements. The third visit (V3) will be scheduled 8 to 10 days after V2 and further follow-up visits every two weeks (i.e. 12 to 16 days after each visit). HbA1c and glycosylated fibronectin, hsCRP, proBNP, Troponin T, will be assessed at V2 as well as at the first visit between 36+0 and 38+6 weeks of gestation (12 ml, non-fasting state) (V4). Detailed fetal ultrasound examinations, a detailed examination of dietary intake as well as a blinded CGM (control group only) will be performed at V2 and V4. Body weight change and use of glucose lowering medications (amount of insulin units) will be examined at every visit. At every follow-up visit glucose measurements (SMBG or rt-CGM) and routine ultrasound examinations (fetal biometry and umbilical artery doppler) will be evaluated by the medical staff and all patients will be treated according to the standard of care for patients with GDM. This includes lifestyle modification and insulin therapy if recommended thresholds are exceeded. Both groups will be treated to be in the target range between 65 to 140 mg/dl [3.6 to 7.8 mmol/l] with at least 8h fasting glucose levels equal or below 95 mg/dl [5.3 mmol/l] and 1h postprandial glucose

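### Caesarean section is compared by a valid but unadjusted chi-square; stratifying on obstetric history taken before randomisation would be a nearly free, optional gain in precision

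*Combined protocol and SAP*

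**What the plan says.** **Test.** Section 3.2 (Analysis plan) states that "Pearson's chi-square test will be used to compare differences in the primary outcome". The same sentence extends that test to further endpoints: "for binary secondary outcomes (such as caesarean section rate, shoulder dystocia and neonatal hypoglycaemia". No baseline covariate enters.

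**Stratified analysis.** The only one for binary outcomes is by centre: "the Cochran-Mantel-Haenszel method will be used as sensitivity analysis to adjust for possible center specific effects".

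**Standing of the outcome.** The Synopsis puts caesarean section in the first-named group: "Differences in neonatal hypoglycemia, rate of caesarean section, shoulder dystocia and neonatal anthropometry will be assessed as secondary outcomes". Neither the Synopsis nor section 1.3 ranks the secondary outcomes.

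**Baseline data.** Section 2.2 lists, at V1, "evaluation of maternal age, parity, history of GDM in previous pregnancies, detailed family history, ethnicity, preconceptional diseases, obstetric history". Previous mode of delivery is not named as an item. On timing it says: "Randomisation will be done after a run-in period of 6 to 8 days (V2"). For women diagnosed before 24+0 the run-in is omitted.

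**Balance by design.** Section 2.4 minimises on gestational week at entry, BMI class and "previous pregnancy with GDM (two strata: yes or no"). Neither parity nor previous caesarean is a factor.

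**The concern.** A previous caesarean is likely to be a strong predictor of how a woman delivers this time. If so, it adds outcome variation that has nothing to do with glucose monitoring. An unadjusted test leaves that variation in the error term. A test stratified on the predictor removes it.

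Two things are at stake. The first is power: section 3.1 sizes the trial on LGA alone, so the power for caesarean section is whatever the chosen analysis can extract from about 169 women per group. The second is interpretation: if the groups happen to differ clearly in previous caesarean, the crude difference carries that imbalance and the plan has no pre-specified analysis to set beside it. The information needed is taken before allocation, so using it is legitimate baseline adjustment, and section 3.2 already names a suitable method.

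**Working it through.** **1. The plan's own figure.** Section 3.1 gives 169 per group for LGA of 13.7% vs 25.8%, two-sided 0.05, 80% power. With pooled variance under the null, n = [1.960·√(2p̄(1−p̄)) + 0.842·√(p₁(1−p₁)+p₂(1−p₂))]² / (p₂−p₁)², with p̄ = 0.1975. This is (1.1035 + 0.4684)² / 0.121² = 168.8, so 169. The figure is reproduced. It concerns LGA only; the documents state neither a rate nor a power for caesarean section.

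**2. Assumed inputs (not from the documents).** q is the share of women with a previous caesarean, a the caesarean risk with that history, b the risk without it. The first row is deliberately weak.

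**3. Variance explained and chance imbalance at 169 per group.**
- Overall rate p = qa + (1−q)b.
- R² = q(1−q)(a−b)² / [p(1−p)].
- Equivalent gain in sample size = 1/(1−R²) − 1.
- SD of the between-group difference in previous caesarean = √(2q(1−q)/169).
- Shift of the crude caesarean difference for a 1-SD imbalance = SD × (a−b).
- Standard error (SE) of the crude difference = √(2p(1−p)/169).

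| q / a / b | p | R² | Gain in N | Imbalance SD (points) | Shift per SD (points) | SE (points) |
|---|---|---|---|---|---|---|
| 10/50/30% | 32.0% | 1.7% | 1.7% | 3.3 | 0.7 | 5.1 |
| 10/70/30% | 34.0% | 6.4% | 6.9% | 3.3 | 1.3 | 5.1 |
| 15/75/28% | 35.1% | 12.4% | 14.1% | 3.9 | 1.8 | 5.2 |
| 20/80/25% | 36.0% | 21.0% | 26.6% | 4.4 | 2.4 | 5.2 |

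Worked example, third row: p = 0.15×0.75 + 0.85×0.28 = 0.3505; R² = 0.1275×0.47² / (0.3505×0.6495) = 0.124; shift = 3.88×0.47 = 1.8 points.

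**4. Simulated power and type I error.** 200,000 trials per cell, 169 per group, simple 1:1 allocation (minimisation not simulated). Each cell shows chi-square, then CMH stratified by previous caesarean (yes/no).

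| q / a / b | Odds ratio 0.5 | Odds ratio 0.75 | Odds ratio 0.5, but no effect after previous caesarean | Type I error |
|---|---|---|---|---|
| 10/50/30% | 77.3 → 77.7% | 21.9 → 22.1% | 64.2 → 65.7% | 5.0, 4.9% |
| 10/70/30% | 74.9 → 77.6% | 21.1 → 21.8% | 62.3 → 66.8% | 5.0, 5.0% |
| 15/75/28% | 70.0 → 75.8% | 19.1 → 20.9% | 51.8 → 59.5% | 5.0, 5.0% |
| 20/80/25% | 61.8 → 72.4% | 16.5 → 19.6% | 39.8 → 50.9% | 4.9, 5.0% |

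The gain is 0.4 to 10.6 points at an odds ratio of 0.5 and 0.2 to 3.1 points at 0.75. An odds ratio of 0.5 means about 11 to 13 fewer caesareans per 100 women in these scenarios.

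**5. Three strata.** A separate simulation (20,000 trials, odds ratio 0.5) split women as nulliparous / parous without previous caesarean / previous caesarean, with assumed rates for the extra stratum. Power rose from 77.6 to 78.0% in the weak case, and in the other three from 74.6 to 77.2%, 68.5 to 74.8% and 58.6 to 70.5%. Type I error was 4.8-5.3%.

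**6. When a large imbalance occurs.** An imbalance beyond 1.5 SD arises in about 2×(1−0.933) = 13% of trials under simple randomisation. Within those trials the chi-square rejected a true null in 5.6%, 7.3%, 8.9% and 12.4% of cases (rows in order); the stratified CMH test stayed at 5.0-5.1%.

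**The case against.** The strongest reply is that an unadjusted test of a secondary outcome in a 1:1 randomised trial is a legitimate pre-specified choice. That stands. A reader might infer that the chi-square is biased or that its error rate is inflated. The documents do not support this: over all randomisations type I error is 5%, and chance imbalance is already allowed for in the test's error rate and interval width. A 1-SD imbalance moves the crude difference by 0.7-2.4 points against a standard error of about 5. The case for correction is conditional on a large imbalance actually occurring.

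The gain also depends wholly on assumed rates and effect. It is negligible if history predicts weakly, and at an odds ratio of 0.75 power stays near 20% whichever test is used. This stands too, and limits the weight of the point.

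A reader might also infer that nothing balances obstetric history. Every woman with previous GDM has had a previous pregnancy, so minimising on that factor balances parity in part and perhaps previous caesarean as well; it does not target the latter. Likewise, being named early in a list does not make caesarean section a key secondary outcome.

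Finally, section 3.2 describes itself as a selection of methods, so an adjusted analysis is not excluded. None is pre-specified, however, and in an open-label trial a covariate chosen after seeing the data is less convincing than one fixed beforehand.

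**Conclusion.** The point holds as a matter of efficiency, not as an error. The planned chi-square for caesarean section is valid. It sets aside a probably strong predictor taken before randomisation, and it leaves a large imbalance in previous caesarean, should one arise, without a planned correction.

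With previous caesarean assumed in 10-20% of women and caesarean risk of 50-80% with it and 25-30% without, stratification at 169 per group is worth roughly 0-11 points of power at an odds ratio of 0.5 and roughly 0-3 points at 0.75. The gain persists, at roughly 2-11 points, if monitoring has no effect after a previous caesarean and the odds ratio is 0.5 otherwise. Where the predictor is weak, the stratified test costs nothing material. All of these sizes rest on assumed rates, and on V1 obstetric history including previous mode of delivery, which section 2.2 does not say.

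This is an optional, nearly free improvement of minor to moderate severity.

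**What to change.** In section 3.2, pre-specify for caesarean section a CMH test stratified by V1 obstetric history: nulliparous / parous without previous caesarean / previous caesarean. Report the Mantel-Haenszel risk difference with its 95% CI, keeping all randomised women in the analysis whatever their history. Keep the Pearson chi-square as the unadjusted companion; the centre-stratified sensitivity analysis need not change.

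In section 2.2 and the case report form, confirm that V1 obstetric history records previous mode of delivery, and name the item.

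Cost: a sentence or two of text. No new data are needed if the item is already recorded; otherwise one baseline field must be added or recovered from the obstetric record. No extra participants are needed and there is no loss of validity. The wording should be fixed before outcome data by group are seen.

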### *1.3. Primary and secondary outcomes*

*Primary objective:* To assess differences in the proportion of LGA newborns (birth weight >90. pct) in women with GDM using rt-CGM as compared to women with GDM using SMBG.

*Secondary objectives:* To assess differences in further obstetric or neonatal complications, neonatal hypoglycaemia, rate of caesarean section, shoulder dystocia and neonatal anthropometry will be assessed as secondary objectives. Further secondary outcomes are: differences in neonatal hyperinsulinemia, rt-CGM measures such as mean interstitial glucose, glycaemic variability, time in range (65 to 140 mg/dl [3.6 to 7.8 mmol/l]) as well as time spent in hyper- and hypoglycaemia (day-time: 07.01 to 22.59hr and night-time: 23.00 to 07.00hr), duration and frequency postprandial hyperglycaemic excursions, start and amount of glucose lowering therapy, HbA1c, glycosylated fibronectin, hsCRP, proBNP, Troponin T, change in bodyweight during pregnancy and after delivery as well as glucose disposal at postpartum (markers of insulin sensitivity, insulin secretion and β-cell function assessed by a postpartum OGTT). Health-related quality of life (HRQoL) is a patient-reported outcome which has become

as important in the evaluation of interventions as patient-relevant clinical outcomes. Therefore, HRQoL will be elicited. In addition, a health economic evaluation in terms of cost-effectiveness and cost-utility analysis will be performed.

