#### *2.10. Fetal biometry*

Parameters of fetal anthropometry as determined by ultrasound as well as neonatal data including length, weight, gestational age at delivery will be included in the final analysis. A detailed fetal ultrasound examination will be performed at V2 and repeated at V4 (between 36+0 to 38+6 weeks of gestation) to assess fetal growth parameters including head circumference, biparietal diameter and abdominal circumference and abdominal fat thickness,

femur length (measured and expressed as standardized gestational age related fetal growth percentiles ), amnion fluid index as well as size and location of the placenta and fetal subcutaneous tissue thickness. Moreover, fetal growth symmetry will be assessed by fetal head to abdomen circumference ratio and fetal doppler measurements (mainly umbilical artery and middle cerebral artery and ductus venosus). Furthermore, fetal hepatic size (all hepatic diameters, such as area and volume) and umbilical venous volume flow and an echocardiatic examination of the fetus will be performed in a subgroup (only study site Vienna).

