### *2.11. Obstetric Outcome*

Obstetric outcome (caesarean section, birth injury, preterm birth before 37 completed weeks of gestation) stillbirth, small for gestational age (birth weight <10. Pct), large for gestational age infant (birth weight >90. Pct), shoulder dystocia, admitted to neonatal intensive care unit umbilical cord blood pH, APGAR score) will be recorded immediately after delivery. Length of hospital stay for mothers and offspring as well as duration of high-level neonatal care, respiratory distress, fetal hyperbilirubinemia and neonatal death ≤28 days will be further assessed. Calculations of age and sex adjusted percentiles will be performed by using international anthropometric standards according to those used in the CONCEPTT study. Neonatal hypoglycaemia is defined as local blood glucose ≤31 mg/dl [1.7 mmol/l] in the first 24h after delivery and ≤45 mg/dl [2.5 mmol/l] after the first 24h after delivery or treatment with glucose infusion according to the HAPO study. Additional anthropometric measures of the offspring include: head, shoulder and abdominal circumference, length, upper and lower arm and leg circumference and skin fold measurements (suprailiac and subscapular, triceps, quadriceps) in accordance with previous studies. Thereby Skinfold measurements will be performed by using a validated instrument (Harpenden Skinfold Caliper) within 48h after delivery (VPP1).

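### Continuous newborn measurements are compared by an unadjusted t-test: valid for the total effect, but less precise than it could be and, for length, circumferences and skinfolds, not matched to the age- and sex-standardised idea behind LGA

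*Combined protocol and SAP*

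**What the plan says.** - **Test.** Section 3.2 lists the continuous secondary outcomes and ends the list with "or anthropometric data of the newborn) will be compared by student's t-test". A rank-based method such as Brunner-Munzel "will be used as an alternative in case of skewed distributed parameters". Neither test takes a covariate, and the section mentions no standardised score for newborn size.
- **Status.** Section 1.3 makes newborn size a secondary objective: "shoulder dystocia and neonatal anthropometry will be assessed as secondary objectives".
- **Primary outcome.** Section 1.3 defines it through a birth-weight percentile: "To assess differences in the proportion of LGA newborns (birth weight >90. pct) in women with GDM".
- **Standardisation.** Section 2.11 says "Calculations of age and sex adjusted percentiles will be performed by using international anthropometric standards". It does not list the measurements this covers. The sentence follows the LGA and SGA definitions and comes before the other newborn measurements.
- **Other measurements.** Section 2.11 continues: "Additional anthropometric measures of the offspring include: head, shoulder and abdominal circumference, length, upper and lower arm and leg circumference and skin fold measurements". No reference standard is attached to these.
- **Gestational age at birth.** Section 2.10 says "neonatal data including length, weight, gestational age at delivery will be included in the final analysis", without saying in what role.
- **Scope of the plan.** Section 3.2 adds that "the present analysis plan represents only a selection of methods, which will be used for analysing the main objectives".

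**The concern.** The trial's idea of overgrowth is size for gestational age and sex. The planned analysis of the continuous newborn data does not carry that idea through. Two things follow.

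First, precision. Newborn size varies with sex, and sex is fixed before randomisation. Leaving it out puts explainable variance into the error term. The same holds for the baseline factors already used in the minimisation.

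Second, the question being answered. An unadjusted difference in, say, abdominal circumference is a difference in size at birth whenever birth occurred. LGA is size for age. The two can be read together only if the plan says which question each analysis answers, and at present it does not. Neonatal anthropometry is the natural continuous companion to LGA, so readers will use it to support or question the primary result.

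**Working it through.** **1. The plan's own figure.** The documents give no sample size or power for newborn measurements, so the only figure to reproduce is the one for LGA in section 3.1.

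n per arm = [z₀.₉₇₅·√(2p̄q̄) + z₀.₈₀·√(p₁q₁ + p₂q₂)]² / (p₁ − p₂)², with p₁ = 0.258, p₂ = 0.137, p̄ = 0.1975

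= [1.960 × 0.5630 + 0.842 × 0.5565]² / 0.121² = 2.471 / 0.01464 = 168.8, so 169 per arm.

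This agrees with the plan (power at 169 per arm is 80.1%). I use 169 per arm below.

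**2. Precision of the unadjusted test.** Detectable difference in SD units at 80% power, two-sided 5%:

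(1.960 + 0.842) × √(2/169) = 2.802 × 0.1088 = 0.305 SD.

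**3. Precision after adjustment.** If covariates explain a share R² of the variance, the detectable difference is multiplied by √(1 − R²). R² is assumed, because the documents give none.

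| R² (assumed) | Detectable difference (SD) | Power for a true 0.25 SD difference | Equivalent n per arm, 169/(1 − R²) |
|---|---|---|---|
| 0 (t-test) | 0.305 | 63% | 169 |
| 0.05 | 0.297 | 65% | 178 |
| 0.10 | 0.289 | 68% | 188 |
| 0.20 | 0.273 | 73% | 211 |
| 0.30 | 0.255 | 78% | 241 |

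**4. Where sex alone falls.** With equal numbers of boys and girls, a sex difference of δ (in SD units) explains R² = δ²/4. An assumed δ of 0.3 gives 0.0225 and a detectable difference of 0.305 × √0.9775 = 0.301 SD. Reaching R² = 0.05 through sex alone needs δ = √0.20 = 0.45. So sex alone belongs near the top of the table. The lower rows need further predictors, such as the minimisation factors or, for birth weight, standardisation for gestational age.

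**5. Validity of the unadjusted test.** In a simulation (3,000 runs, 169 per arm, correlation of 0.5 between size and gestational age at birth, no arm difference in gestational age, no true effect), the t-test rejected in 5.3% of runs. With a true difference of −0.25 SD, its mean estimate was −0.250. It is neither biased nor oversized in that setting.

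**6. When the two questions separate.** If the arms differ in mean gestational age at birth by d SD, and size correlates r with gestational age, the unadjusted difference contains r × d with no difference in size for age. For r = 0.5 and d = 0.2 this is 0.10 SD, and the t-test reaches p ≤ 0.05 in about 15% of trials. Over r = 0.3 to 0.6 and d = 0.1 to 0.3 it is 0.03 to 0.18 SD, and 6% to 38%. All of these are assumed values. They show when the estimands diverge, not that they will.

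**The case against.** The strongest defence is that an unadjusted comparison of randomised arms is not a mistake. It estimates the whole effect of the monitoring strategy on newborn size, including any part that acts through timing of birth. That stands.

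It can also be said that the test might be applied to percentiles. Section 2.11 plans them in general terms, and section 2.10 brings gestational age into the final analysis. For birth weight this is a fair reading, so it cannot be asserted that birth weight will be compared on the gram scale. It is much weaker for length, circumferences and skinfolds, which are listed afterwards as additional measures. The remark that the plan is only a selection of methods does not close the gap, because a test is named for these outcomes.

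A reader might go further and infer that the t-test result will confuse growth with timing of delivery, because staff who know the arm decide when to deliver. The documents do not support that. They give no induction policy, do not say who decides on delivery, and do not suggest that gestational age at birth will differ between arms. Section 2.2 sets the same glucose targets for both arms. Even if timing did differ because of the intervention, the rejection rates in step 6 would be the chance of detecting a real difference in size at birth. They would be false positives only for a size-for-age question.

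It is equally tempting to put gestational age at birth into every model. That variable arises after randomisation. Section 2.2 has fetal biometry evaluated at every follow-up visit. If fetal size influences when women deliver, adjusting for gestational age at birth can itself bias the arm effect.

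**Conclusion.** The point holds as a matter of precision and of stating the question, not of validity. The planned test is sound for the total effect. It gives up some precision by ignoring infant sex and the baseline minimisation factors. For length, circumferences and skinfolds it also leaves the analysis out of line with the age- and sex-standardised concept used for LGA.

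The gain is modest and rests wholly on an assumed R². The fall from 0.305 to 0.297 SD (R² = 0.05) is a reasonable expectation if little beyond sex is predictive; 0.255 SD (R² = 0.30) would require substantially more. One R² need not apply to every measurement. Only secondary outcomes are involved, and the LGA analysis is untouched. It is a cheap improvement.

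**What to change.** Amend section 3.2 as follows:

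1. Analyse birth weight as an age- and sex-standardised z-score from the same standard as LGA. It then answers the same size-for-age question as the primary outcome, and shares its caveat that gestational age at birth is known only after randomisation.
2. Analyse length, circumferences and skinfolds by linear regression on arm, infant sex and the minimisation factors in section 2.4: week of gestation at entry, previous GDM and BMI class. Section 2.4 announces three strata for entry week but lists four ranges, so state which coding is used.
3. Keep the unadjusted difference beside each of these as the total effect.
4. Report gestational age at birth by arm, so that readers can see whether the two questions diverge.
5. Label any model that adjusts for gestational age at birth as a supportive size-for-age analysis, with the reason given.

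The cost is a few lines of analysis-plan wording. Gestational age at delivery and the minimisation factors are already recorded, and infant sex is needed for the planned percentiles. The downside is two estimates per measurement, so the plan should say in advance which one leads.
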